8.6. Multiple Comparisons/Multiplicity

For the primary and key secondary efficacy analyses, the overall 2-sided level of significance will be $\alpha=0.05$. The hypothesis testing of key secondary endpoints will be conducted using a gatekeeping procedure based on a closed fixed-sequence test, provided the primary efficacy endpoint comparison is statistically significant at an alpha level 0.05. If this comparison is not statistically significant, then the comparison of key secondary efficacy endpoints will be considered nominal, descriptive and exploratory. This procedure controls the study-wise type I error and is described below.

1. First placebo and NEOD001 will be compared with respect to the primary efficacy endpoint. If the comparison achieves statistical significance at the 2-sided 0.05 level in favor of NEOD001, then
2. Placebo and NEOD001 will be compared with respect to change from baseline to 12 months of treatment in the SF-36v2 PCS score. If the comparison achieves statistical significance at the 2-sided 0.05 level in favor of NEOD001, then
3. Placebo and NEOD001 will be compared with respect to change from baseline to 12 months of treatment in the 6MWT distance (meters). If the comparison achieves statistical significance at the 2-sided 0.05 level in favor of NEOD001, then
4. Placebo and NEOD001 NT-proBNP slopes over 12 months of treatment will be compared.

If at any step defined above, the comparison is not statistically significant at the 2-sided 0.05 level, then the remaining comparisons in the stated hierarchy will be considered nominal, descriptive and exploratory. The study-wise type I error will be maintained with the above closed procedure.

8.7. Primary Efficacy Analysis

The estimand for NT-proBNP (cardiac) best response is the difference in cardiac best response rate between treatment groups through 12 months of treatment in all randomized subjects with AL amyloidosis who received any amount of drug.

The primary efficacy analysis will test the following hypothesis:

- H_0 : The percentage of NT-proBNP best responders through 12 months of treatment is equal between placebo and NEOD001.
- H_1 : The percentage of NT-proBNP best responders through 12 months of treatment is different between placebo and NEOD001.

The primary efficacy analyses will compare placebo and NEOD001 on the distribution of NT-proBNP (cardiac) best response through 12 months of treatment, at alpha level of 0.05, using a CMH test stratified by the randomization stratification factors. All visits after the first infusion of study drug will be included up to and through the EEOS visit to evaluate 12 months of treatment. The number and percentage, with associated two-sided exact (Clopper-Pearson) 95% CIs, of subjects in each category of best response (response, nonresponse) will be presented by treatment group.

8.7.1. Additional Analyses of the Primary Endpoint

A logistic regression (proportional odds model) will be performed with best response as the dependent variable and factors for treatment group and randomization strata. Estimates of the odds ratio comparing NEOD001 to placebo and the 95% CI of the odds ratio will be presented. An odds ratio greater than 1 favors the NEOD001 treatment group.

Cardiac response as 3 categories (response, stable, and progression) will be analyzed in the same manner described above, except ordinal logistic regression will be used for the analysis of 3 category response.

Cardiac response will also be analyzed according to [Comenzo 2012 \(Appendix 2\)](#), where a decrease ≥ 2 NYHA class from baseline (must have baseline class of 3 or 4) is also considered a response. The same statistical methods described above will be used to evaluate treatment differences.

Cardiac progression will also be analyzed according to [Comenzo 2012 \(Appendix 2\)](#), where subject visits that meet renal progression (defined as an eGFR of < 30 mL/min/1.73 m²) will be excluded. The same statistical methods described above will be used to evaluate treatment differences.

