7. Achieved at least a partial hematologic response (per [Appendix 1](#)) to a first-line therapy resulting in a stable hematologic condition not currently requiring additional active treatment against the PCD component of their AL disease
8. Adequate bone marrow reserve, hepatic and renal function, as demonstrated by:
 - Absolute neutrophil count (ANC) $\geq 1.0 \times 10^9/L$
 - Platelet count $\geq 75 \times 10^9/L$
 - Hemoglobin ≥ 9 g/dL
 - Total bilirubin $\leq 2 \times$ upper limit of normal (ULN)
 - Aspartate aminotransferase (AST) $\leq 3 \times$ ULN
 - Alanine aminotransferase (ALT) $\leq 3 \times$ ULN
 - Alkaline phosphatase (ALP) $\leq 5 \times$ ULN (except for subjects with hepatomegaly and isozymes specific to liver, rather than bone)
 - Estimated glomerular filtration rate (eGFR) ≥ 30 mL/min/1.73 m² as estimated by the Chronic Kidney Disease Epidemiology Collaboration (CKD-EPI) equation
9. Systolic blood pressure (BP) 90-180 mmHg
10. Distance walked during each of the two Screening 6MWTs is >100 meters and <600 meters
11. Women of childbearing potential (WOCBP) must have 2 negative pregnancy tests during Screening, the second within 24 hours prior to the first administration of study drug and must agree to use highly effective physician-approved contraception ([Appendix 2](#)) from Screening to 90 days following the last study drug administration
12. Male subjects must be surgically sterile or must agree to use highly effective physician-approved contraception ([Appendix 2](#)) from Screening to 90 days following the last study drug administration
13. Ability to understand and willingness to sign an ICF prior to initiation of any study procedures

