2.3.3. Additional Secondary Efficacy Endpoints

2.3.3.1. Renal Evaluable Subjects: Renal Best Response from Baseline through 12 Months of Treatment

The Renal Evaluable Population will include subjects who had renal involvement (i.e., proteinuria >0.5 g/24 hours [measured by 24-hour urine total protein excretion]) at baseline and at least one post-baseline assessment of proteinuria. All visits after the first infusion of study drug up and through the EEOS visit will be included to evaluate 12 months of treatment.

For these subjects, renal response categories (modified from Palladini 2014; Appendix 2) are defined as:

Response	Stable	Progression
≥ 30% decrease from baseline or < 0.5g/24 hours post-baseline result of proteinuria (measured by 24-hour urine total protein excretion) in the absence of renal progression	Assessment was neither Response nor Progression	≥ 25% decrease in eGFR from baseline Note: if assessment qualifies as both Response and Progression, then assessments will be counted as progression

Best response is defined as the most favorable category (response, stable, or progression) across all visits. Subjects will be classified as responders or non-responders. Non-response is defined as either stable or progression.

2.3.3.2. Peripheral Neuropathy Evaluable Subjects: Change from Baseline to 12 Months of Treatment in Neuropathy Impairment Score–Lower Limbs (NIS-LL) Total Score

The Peripheral Neuropathy Evaluable Population will include subjects who had peripheral nerve involvement at baseline (only if the subject had ascending sensorimotor neuropathy due to AL amyloidosis etiologies at screening answered as yes) and had a baseline NIS-LL score of 2 or greater and at least one post-baseline peripheral neuropathy assessment. All visits will be included in the model (Section 8.9.2), with the primary comparison at the EEOS visit to evaluate 12 months of treatment.

NIS-LL is a scoring system graduated from 0 points to a maximum of 88 points (the absence of all motor, sensory, and reflex activity in the lower extremities) (Dyck 1995; Appendix 3). The

scale is additive of all deficits (64 potential points for muscle strength, 8 points for reflexes, and 16 points for sensory function) in the lower extremities. The component scores will be calculated by summing the values of the following assessments:

- Sensory Function (in the great toe) = Sum of (touch pressure, pinprick, vibration, joint position)
- Reflexes = Sum of (knee, ankle)

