8.10.7.2. Cardiac Progression-Free Survival

Cardiac progression is defined as NT-proBNP progression of >30% increase and >300 ng/L increase or death. Cardiac progression will not be evaluated in the presence of renal progression, defined as an eGFR of < 30 mL/min/1.73 m², according to [Comenzo 2012 \(Appendix 2\)](#).

Progression-free survival is defined as the time from first infusion of study drug to the earliest of:

- first documented date of disease progression (as defined by NT-proBNP [Section 2.3.4.1.1]) or
- withdrawal from treatment or study due to organ (cardiac) progression or
- death on the study or
- death following withdrawal from treatment due to any cause.

Progression-free survival will be calculated in days as the earliest of the above dates (disease progression or death) minus the date of first infusion of study drug plus 1.

Subjects who are alive with no documented progression prior to the end of the study will be censored at the earliest of their date of the first assessment that meets renal progression (defined as an eGFR of < 30 mL/min/1.73 m²), date of the last NT-proBNP measurement, or date they withdraw consent or are lost to follow-up.

NEOD001 will be compared to placebo using the log rank test stratified by the randomization stratification factors. KM estimates of the distribution of the time-to-event will be tabulated and graphed by treatment group. The tabulation will include the KM estimate of the medians, 25th and 75th percentiles, and corresponding 95% CIs, if estimable. The tabular and graphical summaries will include the at-risk counts for every visit. The number and percent of subjects

censored and with events will be presented overall and for each visit, using last day of the visit window. The hazard ratio and 95% CI will be determined based on a Cox regression model stratified by randomization strata to estimate the magnitude of the effect.

In addition, a sensitivity analysis will be performed counting death or progression without subsequent response as an event.

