10. CHANGES TO PROTOCOL PLANNED ANALYSES

Per Protocol A3, Section 8.3.4: “All exploratory quantitative endpoints, except the 6MWT.... will be analyzed in the same manner described for the SF-36v2...”. The exploratory analyses of LVEF are performed per Section 8.10.1.2 of this SAP.

Appendix 4 of the protocol, footnotes a and b, state “In addition to the progression criteria listed above, the investigators will use their best clinical judgment in circumstances that do not meet the specifically referenced criteria above in assessing the progression. A repeated assessment at an interval that is determined by the investigator is required to confirm the progression.” and “Subjects with progressively worsening renal function cannot be scored for NT-proBNP progression.” Repeat assessments were only done using local laboratories and therefore not included in the central laboratory data for inclusion in analyses. In addition, per the SAP renal progression is not considered for the primary endpoint analyses and is only included as a sensitivity analysis.

Renal endpoints other than renal response will be repeated for the ITT population.

The Safety Population was updated to use treatment received for all subjects instead of randomized treatment.

The following endpoints were removed:

- Time to eGFR ≤ 15 mL/min/1.73 m² (Chronic Kidney Stage 5)
- Time to doubling of creatinine
- Time to peripheral neuropathy organ progression
- Time to peripheral neuropathy organ response
- Time to hepatic organ progression
- Time to hepatic organ response
- Hematologic response at each visit
- Hematologic best response through 3, 6, 9, and 12 months of treatment
- Mayo Clinic Stage including any subgroup analyses
- Peripheral neuropathy best response through 3, 6, 9, and 12 months of treatment

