APPENDIX 2. ORGAN RESPONSE AND PROGRESSION CRITERIA

Organ	Response	Progression
Heart/Cardiac ^{a,b}	NT-proBNP response (>30% and >300 ng/L decrease in subjects with baseline NT-proBNP \geq 650 ng/L) OR NYHA class response (\geq 2 class decrease in subjects with baseline NYHA class III or IV) ^b	NT-proBNP progression (>30% and >300 ng/L increase) ^c
Renal ^d	\geq 30% decrease in proteinuria or drop of proteinuria below 0.5 g/24 hours in the absence of renal progression	\geq 25% decrease in eGFR
Peripheral Nerve ^f	NIS-LL increase from baseline of <2 points	NIS-LL increase from baseline of \geq 2 points
Liver/Hepatic ^{a,e}	50% decrease in ALP value from baseline OR \geq 2 cm reduction in liver size radiographically ^e	\geq 50% increase in ALP from baseline

Abbreviations: ALP = alkaline phosphatase; eGFR = estimated glomerular filtration rate; NIS-LL = Neuropathy Impairment Score–Lower Limbs; NT-proBNP = N-terminal pro brain natriuretic peptide; NYHA = New York Heart Association.

a Modified from Table 2 in [Comenzo 2012](#).

b NYHA class not considered for primary efficacy endpoint analyses.

c Subjects with progressively worsening renal function cannot be scored for NT-proBNP progression.

d [Palladini 2014](#).

e Liver size was not collected and is therefore not considered for evaluation of hepatic response.

f [Coelho 2012](#).

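### The SAP drops or censors NT-proBNP progression on a fixed eGFR level (<30), but the appendix it cites defines renal progression by change (≥25% fall); the two rules classify different visits

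*SAP*

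**What the plan says.** Four places in the SAP bear on how kidney function enters the scoring of cardiac progression.

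- **SAP 8.7.1** adds an analysis introduced by "Cardiac progression will also be analyzed according to" the cited consensus guideline and Appendix 2. It leaves out visits, in its words, "where subject visits that meet renal progression (defined as an eGFR of < 30" mL/min/1.73 m²).
- **SAP 8.10.7.2** (cardiac progression-free survival) makes the same link to the guideline and Appendix 2: "Cardiac progression will not be evaluated in the presence of renal progression, defined as an eGFR of < 30" mL/min/1.73 m². Among subjects alive without documented progression, the first assessment below 30 is also one of the candidate censoring dates, and the earliest candidate applies.
- **SAP Appendix 2** has no level of 30. Its renal row sets progression at or above a "25% decrease in eGFR". Footnote c, attached to the cardiac progression cell, reads: "Subjects with progressively worsening renal function cannot be scored for NT-proBNP progression". Protocol Appendix 4 carries the same footnote.
- **SAP 2.3.3.1** (renal best response) again sets renal progression at or above a "25% decrease in eGFR from baseline".

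SAP Section 10 lists departures from the protocol. It repeats the worsening-renal-function footnote and then states that "renal progression is not considered for the primary endpoint analyses and is only included as a sensitivity analysis". It does not mention or justify the <30 level.

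**The concern.** NT-proBNP progression is itself a change from baseline (a rise of >30% and >300 ng/L). The footnote exists so that a rise accompanying renal decline is not counted as cardiac worsening. That calls for a rule about renal change. A fixed level asks instead whether eGFR is low, which depends on where the subject started as well as on how far eGFR has moved.

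The same term therefore has two definitions in one SAP. In 8.10.7.4 the renal component of time to cardiac or renal progression follows the ≥25% rule through 8.9.1, while the PFS analysis two sections before it uses <30. At stake is whether these secondary looks at cardiac progression can show that renal decline does not explain the NT-proBNP rises, and whether PFS censoring falls mainly on subjects who entered with the lowest eGFR.

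**Working it through.** **1. The plan's own figure.** Inputs from SAP Section 3: response rates 50% and 22.5%, two-sided α = 0.05, N about 130 (65 per arm). Using the pooled-variance formula, with p̄ = (0.50 + 0.225)/2 = 0.3625:

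- Null SE = √(2 × 0.3625 × 0.6375 / 65) = 0.0843
- Alternative SE = √((0.25 + 0.1744) / 65) = 0.0808
- z = (0.275 − 1.96 × 0.0843) / 0.0808 = 1.36, so power = 91.3%

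The stated 91% reproduces. At 50 per arm the same formula gives 82.6%, matching >80%. The renal rule does not enter this calculation: SAP 2.3.1 counts stable and progression alike as non-response, and Section 10 keeps renal progression out of the primary analysis.

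**2. The two renal rules.** Let b be baseline eGFR.

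- Level rule (8.7.1, 8.10.7.2): eGFR < 30
- Change rule (2.3.3.1, Appendix 2 renal row): eGFR ≤ 0.75 × b

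They cross where 0.75 × b = 30, that is, at b = 40. Inclusion criterion 8 requires eGFR ≥30 "as estimated by the Chronic Kidney Disease Epidemiology Collaboration (CKD-EPI) equation", so subjects can enter on either side of 40. The baselines below are illustrative.

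| Baseline | 25% fall reached at | Fall that must be exceeded to go below 30 | Visits on which the rules differ |
|---|---|---|---|
| 31 | 23.25 | 1/31 = 3.2% | above 23.25 and below 30: only the level rule excludes |
| 35 | 26.25 | 5/35 = 14.3% | above 26.25 and below 30: only the level rule excludes |
| 40 | 30 | 10/40 = 25% | exactly 30 only |
| 60 | 45 | 30/60 = 50% | 30 to 45: only the change rule excludes |
| 80 | 60 | 50/80 = 62.5% | 30 to 60: only the change rule excludes |
| 90 | 67.5 | 60/90 = 66.7% | 30 to 67.5: only the change rule excludes |

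**3. Worked cases.**

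- 80 to 50: (80 − 50)/80 = 37.5%. This is renal progression under 2.3.3.1 but not under 8.7.1 or 8.10.7.2. A concurrent NT-proBNP rise of >30% and >300 ng/L is scored as cardiac progression and is a PFS event.
- 90 to 35: (90 − 35)/90 = 61.1%. Same outcome.
- 31 to 29: (31 − 29)/31 = 6.5%. Not renal progression under 2.3.3.1, yet the visit is dropped in 8.7.1 and, absent documented progression, PFS can be censored there.

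**4. Baseline below 30.** Eligibility is judged at screening, but SAP 2.2.7 takes baseline as the last value before the first infusion, and Section 6 plans a baseline eGFR <30 subgroup. Such a subject could meet the level rule at the first post-baseline visit with no decline at all.

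**5. Other analyses.** Duration of cardiac response (8.10.7.3) and time to cardiac progression (8.10.7.4) state no renal exclusion, despite footnote c.

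**The case against.** The strongest defence is that the two rules have different jobs and sources. The 25% figure is in the renal row of Appendix 2, is attributed to a different paper, and defines a renal efficacy endpoint. What governs cardiac scoring is footnote c, which has no number. Sections 8.7.1 and 8.10.7.2 cite the consensus guideline behind the cardiac row, and <30 may come from it. The level is also written out in both places, so a programmer would know what to code. And a single-visit 25% fall does not by itself show progressive worsening.

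Much of this stands. A reader might infer that Appendix 2 itself bars cardiac scoring after a 25% fall; it does not say so. Whether the guideline supports <30 cannot be settled from the documents. A reader might also infer that every large renal decline goes unfiltered, or that censoring ignores change altogether. Neither is right: any fall to below 30 is caught, and a subject starting at 60 must lose more than 50% to be censored.

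What does not stand is that the choice is merely a preference. The sections claim to apply Appendix 2. Both renal statements there concern change, and Section 10 treats the footnote as a matter of renal progression, a term the SAP elsewhere quantifies as ≥25%. A fixed level departs from that without disclosure.

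The effect in 8.7.1 is also small for best response: a subject is classed as progression only if no visit is stable or better, so rescoring one visit seldom changes the class.

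**Conclusion.** The inconsistency is real and minor. The level rule misses falls of 25% or more that stay at or above 30, which requires baseline eGFR of at least 40. It removes near-stable visits for subjects starting at 30 to below 40.

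The reach is the 8.7.1 additional analysis, the by-visit progression analyses that 8.10.1.1 routes through it, and exploratory cardiac PFS, where event and censoring status can change. A reader might infer that the primary result is at risk. The documents rule that out: the primary CMH test, its 91% power and the fixed-sequence testing of key secondary endpoints do not use the rule.

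The documents give no baseline eGFR distribution, so neither the number of subjects affected nor any direction of bias between arms can be stated. The conclusion rests on taking footnote c, as Section 10 does, to concern renal progression, and on ≥25% being the SAP's only quantified change-based definition of it.

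**What to change.** Before unblinding:

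1. In 8.7.1 and 8.10.7.2, define the renal exclusion (and, for PFS, the renal censoring date) as a decrease in eGFR of at least 25% from baseline, matching 2.3.3.1.
2. Keep the <30 version as a sensitivity analysis, and state in Section 10 that it departs from Appendix 2 and why.
3. Apply the same exclusion to cardiac progression in 8.10.7.3 and 8.10.7.4, and make footnote c point to the chosen definition.

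The cost is SAP wording and some repeat runs. No new data are needed: eGFR is in the chemistry panel (SAP Appendix 10), which is scheduled at every treatment visit. The downside is that visits below 30 with a fall of less than 25% would be scored in the main version; the retained <30 analysis shows how much that matters.

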8.8. Key Secondary Efficacy Analyses

Key secondary efficacy endpoints are described in Section [2.3.2](#), multiplicity adjustments in Section [8.6](#), and missing data conventions in Section [8.2](#).

A plot of the EEOS change from baseline values will be presented. If visual inspection of the data finds the normality assumption is violated, a non-parametric rank analysis of covariance model (ANCOVA) including fixed effects for randomization strata and treatment group, with the ranked baseline value included as a covariate will be used and the Hodges-Lehman estimate of the median treatment difference with associated 95% CI will be presented. A plot of the EEOS change from baseline ranks will be presented. If visual inspection of the ranks finds the normality assumption is violated, the change from baseline at EEOS in SF-36v2 PCS score will be analyzed using a van Elteren test with stratification by randomization strata.

Estimates of least-square (LS) means, standard errors (StdErr), and 95% CIs will be presented by treatment group. In addition, the LS mean difference comparisons between each NEOD001 and placebo, the StdErr of the difference, and 95% CI of the difference will be presented.

Descriptive statistics for SF-36v2 PCS scores, change from baseline, and percent change from baseline will be presented by visit for each treatment group. Mean SF-36v2 PCS scores with associated standard deviation error bars will be plotted by treatment group over time. LS mean change and percent change from baseline in SF-36v2 PCS score with associated StdErr bars will be plotted by treatment group over time. In addition, the cumulative distribution of change from baseline at the EEOS visit will be plotted.

8.8.2. 6MWT Distance to 12 Months of Treatment

The estimand for the 6MWT is the median difference in 6MWT distance change from baseline between treatment groups after 12 months of treatment in all randomized subjects with AL amyloidosis who received any amount of study drug.

The key secondary efficacy analysis will test the following hypotheses:

- H_0 : The distribution of change from baseline in 6MWT distance (meters) after 12 months of treatment is equal between placebo and NEOD001.
- H_1 : The distribution of change from baseline in 6MWT distance (meters) after 12 months of treatment is different between placebo and NEOD001.

For the primary analysis of 6MWT, subjects will be ranked as follows ordered from worst to best:

1. Subjects who died prior to EEOS where time to death is used to rank earlier deaths worse than later deaths
2. Subjects who are missing EEOS and vital status is unknown at EEOS where duration on study is used to rank shorter duration worse than longer duration will be ranked according to time on study drug from worst (shortest time) to best (longest time)
3. Subjects who are missing EEOS because the subject physically cannot perform the test, due to physical incapacity or other reason where duration on study is used to rank shorter duration worse than longer duration will be ranked according to time on study drug from worst (shortest time) to best (longest time)
4. Subjects who are missing EEOS and are known to be alive where duration on study is used to rank shorter duration worse than longer duration will be ranked according to time on study drug from worst (shortest time) to best (longest time)
5. Completed subject's values will be ranked from worst (lowest distance) to best (highest distance) performance

Sensitivity analyses to assess the effect of missing data are specified in Section 8.2.

Descriptive statistics for 6MWT distance, change from baseline, and percent change from baseline will be presented by visit for each treatment group. The change from baseline at EEOS in 6MWT distance (meters) will be analyzed using a rank ANCOVA model including fixed effects for randomization strata and treatment group, with the ranked baseline value included as a covariate. The Hodges-Lehman estimate of the median treatment difference with associated 95% CI will be presented.

The rank ANCOVA assumes the ranked data are normally distributed and homogenous variance. A plot of the EEOS change from baseline ranks and the baseline ranks will be presented. If visual inspection of the ranks finds the normality assumption is violated, the change from baseline at EEOS in 6MWT distance (meters) will be analyzed using a van Elteren test with stratification by randomization strata.

Only valid assessments 6MWT distance will be included in analysis. Reasons for results being invalid will be presented in a listing and will be finalized prior to database lock. Reasons for results being invalid may include:

- Incorrect course length
- Use of unapproved course
- Unapproved administrator of test
- A site staff member has stopped the stopwatch either inadvertently or incorrectly before the 6 minutes are complete and the subject is still able to walk

In addition, the cumulative distribution of change from baseline at EEOS will be plotted for each treatment group.

The percent change from baseline will be analyzed in the same manner.

In addition to the planned sensitivity analyses for handling of missing data (Section 8.2), subjects who have invalid tests recorded will be used (as if the test was completely correctly) instead of being considered as missing.

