8.3.2 Key Secondary Efficacy Analyses

NEOD001 and placebo will be compared on change from baseline in the SF-36v2 PCS score after 12 months of treatment using a REML-based MMRM model including fixed effects for randomization strata, treatment group, categorical time point, and the treatment group \times time point interaction, and with the baseline value included as a covariate. The unstructured covariance model will be used. The Kenward and Roger method will be used to calculate the denominator degrees of freedom for the test of fixed effects. All visits will be included in the model, with the primary comparison at the EOS Visit to evaluate 12 months of treatment.

The NEOD001 and placebo distributions of change from baseline in 6MWT distance (meters) after 12 months of treatment will be analyzed using a van Elteren test with stratification by randomization strata.

The analysis of NT-proBNP will be performed using a general linear mixed effects model to compare the rate of change (i.e., slope) of NT-proBNP over 12 months of treatment between treatment groups. The null hypothesis of no difference in slopes between the treatment groups will be determined by testing the significance of the treatment group by time interaction term.

For the primary and key secondary efficacy analyses, the overall 2-sided level of significance will be $\alpha=0.05$. The hypothesis testing of key secondary endpoints will be conducted in a sequential closed testing gate-keeping procedure separately, provided the primary efficacy endpoint comparison is statistically significant at an alpha level 0.05. If this comparison is not statistically significant, then the comparison of key secondary efficacy endpoints will be considered nominal, descriptive, and exploratory. This procedure controls the study-wise type I error and is described below.

1. First placebo and NEOD001 will be compared with respect to the primary efficacy endpoint. If the comparison achieves statistical significance at the 2-sided 0.05 level in favor of NEOD001, then
2. Placebo and NEOD001 will be compared with respect to change from baseline to 12 months of treatment in the SF-36v2 PCS score. If the comparison achieves statistical significance at the 2-sided 0.05 level in favor of NEOD001, then

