3. SAMPLE SIZE JUSTIFICATION

For the primary endpoint, the assumed true rates for NEOD001 vs placebo are 50% and 22.5%, respectively. Based on a two-sample comparison of proportions at the $\alpha=0.05$ level of significance, a total sample size of 100 subjects (50 in the NEOD001 arm, 50 in the placebo arm) will provide $>80\%$ power based on a two-sided Cochran-Mantel-Haenszel (CMH) test. Based on the actual enrolled sample size ($N\sim 130$), the final power is 91%.

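### SF-36v2 PCS, the test that gates 6MWT and NT-proBNP slope, can change from MMRM to rank ANCOVA to van Elteren on an undefined visual check, so the type I error control claimed in SAP 8.6 is not guaranteed

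*SAP*

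**What the plan says.** Protocol 8.3.2 gives PCS a single analysis: "NEOD001 and placebo will be compared on change from baseline in the SF-36v2 PCS score after 12 months of treatment using a REML-based MMRM model". It has no fallback.

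SAP 8.8.1 keeps that MMRM as the starting point, with an estimand and null hypothesis stated in terms of mean change. It then adds two switches:

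- The changes at the Efficacy End of Study (EEOS) visit are plotted. "If visual inspection of the data finds the normality assumption is violated", the test becomes a rank ANCOVA, reported with a Hodges-Lehmann median difference.
- The ranks are plotted. "If visual inspection of the ranks finds the normality assumption is violated, the change from baseline at EEOS in SF-36v2 PCS score will be analyzed" by a van Elteren test.

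SAP 8.6 places PCS second in a fixed sequence, after the primary endpoint and before 6MWT and NT-proBNP slope. Each gate has the form "If the comparison achieves statistical significance at the 2-sided 0.05 level in favor of NEOD001, then" the next test is done. The section concludes: "The study-wise type I error will be maintained with the above closed procedure".

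SAP Section 10, which lists changes to the protocol's planned analyses, does not mention the PCS switches. SAP 8.8.2 has a similar arrangement for 6MWT: rank ANCOVA first, then van Elteren after a visual check of the ranks. Protocol 8.3.2 names van Elteren alone for 6MWT, and Section 10 is silent on that difference too.

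**The concern.** A fixed sequence controls error when each step has one determinate p-value. Here three tests are named for the PCS step, and the rule for choosing among them is a judgement on outcome data. The SAP does not say what counts as a violation, who decides, whether the plot is pooled over arms, or whether the decision comes before unblinding. It does set timing for other judgement calls: important protocol deviations are settled before lock and unblinding (SAP 5 and 7.6), and reasons for invalid 6MWT results before lock (SAP 8.8.2).

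Three further problems follow from the text:

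- **The check on the ranks cannot work.** Untied ranks have a flat distribution by construction, so looking at them says nothing about the data.
- **The target changes.** The hypothesis is about means, but the fallbacks test ranks at one visit, whereas the MMRM uses all visits.
- **Multiple imputation is not carried through.** SAP 8.2.3.2 describes pooling 10 imputed datasets for the MMRM's least-squares mean difference. Nothing says how the plot is judged, or how rank results are combined, across those datasets.

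The first switch is not a remote contingency. Deaths receive the worst EEOS score in the population, which lengthens the lower tail of the changes. At stake are the PCS claim and the two tests behind it.

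**Working it through.** **1. The plan's own figure.** The SAP gives no operating characteristic for PCS, only for the primary endpoint. SAP Section 3 states that "the assumed true rates for NEOD001 vs placebo are 50% and 22.5%, respectively", with about 130 subjects (65 per arm) and 91% power. Use the pooled-variance formula, power = Φ[(d − 1.96·√(2p̄(1−p̄)/n)) / √((p₁(1−p₁)+p₂(1−p₂))/n)], with d = 0.275 and p̄ = 0.3625:

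- n = 65: (0.275 − 1.96 × 0.0843)/0.0808 = 1.358, so power is 91.3%. This reproduces the stated 91%.
- n = 50: (0.275 − 1.96 × 0.0961)/0.0921 = 0.940, so power is 82.6%. This agrees with the stated figure of more than 80%.

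**2. The check on the ranks.** For untied ranks 1 to n, excess kurtosis is −6(n²+1)/[5(n²−1)]. At n = 130 this is −1.2 × 16901/16899 = −1.2001, whatever the original data. A Shapiro-Wilk test on the ranks 1 to 130 gives p = 0.0003. Deaths share one imputed score but have different baselines, so ranks of the changes stay largely untied. Read literally, the second check always fails, and the path runs from MMRM straight to van Elteren.

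**3. Type I error for PCS.** Simulation under no PCS effect, 10,000 trials per row, N = 130, 1:1 within four strata. The following are assumptions, because the documents give no trial SD, effect size or dropout rate for PCS:

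- baseline SD 10 (the population norm in SAP 2.3.2.1) and residual scale 7
- normal, t with 3 df, or skewed residuals
- 0, 5 or 10% of subjects set to the worst score as deaths
- ANCOVA at EEOS standing in for the MMRM contrast
- Shapiro-Wilk p < 0.05 on pooled changes standing in for the first visual check

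Percent of null trials rejecting at two-sided 0.05; the second-last column counts only rejections favouring NEOD001 (nominal 2.5):

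| Residuals, deaths | ANCOVA | Rank ANCOVA | van Elteren | Mechanical path to van Elteren | Best of ANCOVA and van Elteren | Best of three | Best of three, favouring NEOD001 | First check fails |
|---|---|---|---|---|---|---|---|---|
| Normal, 0% | 4.78 | 4.70 | 4.96 | 4.83 | 6.87 | 7.54 | 3.84 | 4.88 |
| Normal, 5% | 4.77 | 4.86 | 4.75 | 4.72 | 7.13 | 7.97 | 3.88 | 86.19 |
| Normal, 10% | 5.05 | 5.20 | 5.31 | 5.23 | 7.62 | 8.34 | 4.10 | 96.77 |
| t3, 0% | 4.62 | 5.29 | 5.00 | 5.12 | 7.45 | 8.78 | 4.23 | 81.28 |
| t3, 5% | 5.05 | 4.98 | 5.15 | 5.16 | 8.30 | 9.49 | 4.73 | 99.13 |
| Skewed, 0% | 4.98 | 5.03 | 4.93 | 4.93 | 7.71 | 8.92 | 4.47 | 99.87 |
| Skewed, 5% | 4.96 | 5.14 | 4.82 | 4.82 | 7.83 | 9.08 | 4.71 | 100 |
| Skewed, 10% | 4.74 | 4.81 | 4.69 | 4.69 | 7.82 | 9.07 | 4.67 | 100 |

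Stopping the mechanical path at rank ANCOVA instead gives 4.76–5.38%. The simulation standard error near 5% is √(0.05 × 0.95/10,000) = 0.22 percentage points. Separate simulations of the same kind, also on assumed distributions, gave 4.3–5.8% for the mechanical path and 3.5–4.9% for best-of-three claims favouring NEOD001.

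**4. Effect on the family.** With a real primary effect and independence of the two tests, the chance of passing the primary and then falsely rejecting PCS (two-sided) is:

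- one fixed test: 0.913 × 5% = 4.6%
- best of three: 0.913 × 7.54% = 6.9% up to 0.913 × 9.49% = 8.7%

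If the primary null is also true, the primary gate caps the family error at 5% however PCS is tested.

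**The case against.** The strongest defence is that the tests and their order are written down, in a SAP that protocol Section 8 requires to be approved before lock and unblinding. The trigger is distributional shape, not a p-value, and step 3 shows that following the path mechanically on pooled data does no material harm. All of that stands, and it limits the finding. It does not cure the undefined trigger: protocol Section 8 fixes when the SAP is approved, not when or by whom the plot is read.

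A reader might go further than the documents allow in four ways:

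- **That PCS type I error is 7–9% under this plan.** Those rates come from letting the most favourable test stand. The SAP does not describe that procedure; it only fails to exclude it. They also count rejections in both directions, whereas a gate opens only in favour of NEOD001.
- **That study-wise control is broken.** Excess error needs both a real primary effect and a choice influenced by unblinded results.
- **That three tests are always in play.** Under a literal reading of the rank check only MMRM and van Elteren remain, and the worst case falls to 6.9–8.3% two-sided. The flat-ranks defect removes discretion at the second switch.
- **That the mean comparison is dropped.** SAP 8.8.1 presents least-squares means, their difference and confidence intervals without condition. The mismatch with the estimand concerns the deciding test only.

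**Conclusion.** The point holds in a limited form. SAP 8.8.1 leaves open which test yields the PCS p-value, departs from protocol 8.3.2 without recording it, and includes a normality check on ranks that is invalid as written. The fallback tests also do not match the stated mean-based null hypothesis.

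The control claimed in SAP 8.6 is therefore not guaranteed, which is different from lost. PCS type I error stays near 5% if the check is mechanical and on pooled data. If the choice is influenced by unblinded results and the primary effect is real, false PCS claims for NEOD001 could reach about 3.5–4.9% against 2.5% nominal. The two-sided equivalent is about 7% (best of two tests) to 9.5% (best of three) against 5%.

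These ranges rest on assumed residual shapes, SDs and death rates, and on ANCOVA in place of the MMRM with multiple imputation. The invalid rank check, the missing criterion and the Section 10 omission need no assumptions.

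**What to change.** - **SAP 8.8.1:** name the protocol's MMRM on the imputed data as the only PCS test in the hierarchy. Delete both visual-inspection switches. Keep rank ANCOVA and van Elteren as sensitivity analyses; SAP 8.2.4.1 already uses ranking methods that way for PCS.
- **SAP 8.8.2:** likewise fix one 6MWT test (the protocol names van Elteren) and delete the visual check on the ranks.
- **SAP Section 10:** list any departure from protocol 8.3.2 that remains.

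An objective criterion applied to pooled, blinded data before unblinding would also close the gap. It would need a matching estimand and a rule for combining rank results across imputations, so fixing the MMRM is simpler.

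The cost is SAP wording, with no new data or analyses, but it must be done before unblinding to be credible. The small downside is losing an automatic fallback if PCS changes are markedly non-normal; the sensitivity analyses cover that.
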